9.5.2 Safety Analysis Populations

The APaT population will be used for the analysis of safety data in this study. The APaT population consists of all randomized participants who received at least 1 dose of study intervention. Participants will be included in the treatment group corresponding to the study intervention they actually received for the analysis of safety data using the APaT population. For most participants, this will be the study intervention group to which they are randomized. Participants who receive incorrect study intervention for the entire treatment period will be included in the treatment group corresponding to the study intervention actually received.

Any participant who receives the incorrect study intervention for 1 or more cycles but receives the correct study intervention for the remaining cycles will be analyzed according to the participant's randomized treatment group, and a narrative will be provided for any events that occur during the cycle for which the participant was incorrectly dosed.

At least 1 laboratory or vital sign measurement obtained after at least 1 dose of study intervention is required for inclusion in the analysis of each specific parameter. To assess change from baseline, a baseline measurement is also required.

Participants in Part 1 and Part 2 will be analyzed separately.

9.5.3 PRO Analysis Populations

The PRO analyses are based on the PRO FAS population, defined as all randomized participants who have at least one PRO assessment available for the specific endpoint and have received at least one dose of the study intervention. Participants will be analyzed in the treatment group to which they are randomized.

PRO analyses will be performed in Part 2 participants only.

9.6 Statistical Methods

Statistical testing and inference for safety analyses are described in Section 9.6.2. Efficacy results that will be deemed to be statistically significant after consideration of the Type I error control strategy are described in Section 9.8, Multiplicity. Nominal p-values will be computed for other efficacy analyses but should be interpreted with caution due to potential issues of multiplicity.

9.6.1 Statistical Methods for Efficacy Analyses

Efficacy analyses will be performed in Part 2 participants only. This section describes the statistical methods that address the primary and secondary objectives. Methods related to exploratory objectives will be described in the sSAP.

The stratification factors used for randomization (see Section 6.3.2) will be applied to all stratified analyses, in particular, the stratified log-rank test, stratified Cox model, and stratified M&N method. If there are small strata, for the purpose of analysis, strata will be combined to ensure sufficient number of participants, responses and events in each stratum. Details regarding the pooling strategy will be prespecified in the sSAP prior to the database lock for any efficacy IA or final analysis when each applicable endpoint will be analyzed, and decisions regarding the pooling will be based on a blinded review of response and event counts by stratum.

Response or progression in the Second Course phase will not count toward the PFS, OR, and DOR analyses in this study.

9.6.1.1 Overall Survival

The nonparametric Kaplan-Meier method will be used to estimate the survival curves. The treatment difference in survival will be assessed by the stratified log-rank test. A stratified Cox proportional hazard model with Efron's method of tie handling will be used to assess the magnitude of the treatment difference (ie, HR). The HR and its 95% CI from the Cox model with a single treatment covariate will be reported. The stratification factors used for randomization (see Section 6.3.2) will be applied to both the stratified log-rank test and the stratified Cox model. Participants without documented death at the time of analysis will be censored at the last known alive date.

9.6.1.2 Progression-free Survival

The nonparametric Kaplan-Meier method will be used to estimate the PFS curve in each treatment group. The treatment difference in PFS will be assessed by the stratified log-rank test. A stratified Cox proportional hazard model with Efron's method of tie handling will be used to assess the magnitude of the treatment difference (ie, HR) between the treatment groups. The HR and its 95% CI from the stratified Cox model with Efron's method of tie handling and with a single treatment covariate will be reported. The stratification factors used for randomization (see Section 6.3.2) will be applied to both the stratified log-rank test and the stratified Cox model.

Because disease progression is assessed periodically, PD can occur any time in the time interval between the last assessment where PD was not documented and the assessment when PD is documented. The true date of disease progression will be approximated by the earlier of the date of the first assessment at which PD is objectively documented per RECIST 1.1 by BICR and the date of death. Death is always considered as a confirmed PD event. To evaluate the robustness of the PFS endpoint per RECIST 1.1 by BICR, 1 primary and 2 sensitivity analyses with a different set of censoring rules will be performed.

For the primary analysis, any participant who experiences an event (PD or death) immediately after 2 or more missed disease assessments will be censored at the last disease assessment prior to the missed visits. In addition, any participant who initiates new anticancer therapy prior to documented progression will be censored at the last disease assessment prior to the initiation of new anticancer therapy. Participants who do not start new anticancer therapy and who do not experience an event will be censored at the last disease assessment. If a participant meets multiple criteria for censoring, the censoring criterion that occurs earliest will be applied. Sensitivity analyses will be performed for comparison of PFS based on investigator's assessment.

To evaluate the robustness of the PFS endpoint per RECIST 1.1 by BICR, 2 sensitivity analyses with different sets of censoring rules will be performed. The first sensitivity analysis follows the intention-to-treat principle. That is, PDs/deaths are counted as events regardless of missed study visits or initiation of new anticancer therapy. The second sensitivity analysis considers discontinuation of treatment due to reasons other than CR or initiation of new anticancer treatment, whichever occurs later, to be a PD event for participants without documented PD or death. If a participant meets multiple criteria for censoring, the censoring criterion that occurs earliest will be applied.

The censoring rules for primary and sensitivity analyses are summarized in Table 14.

Table 14 Censoring Rules for Primary and Sensitivity Analyses of PFS

Situation	Primary Analysis	Sensitivity Analysis 1	Sensitivity Analysis 2
PD or death documented after ≤1 missed disease assessment, and before new anticancer therapy, if any	Progressed at date of documented PD or death	Progressed at date of documented PD or death	Progressed at date of documented PD or death
PD or death documented immediately after ≥2 consecutive missed disease assessments or after new anticancer therapy, if any	Censored at last disease assessment prior to the earlier date of ≥2 consecutive missed disease assessment and new anticancer therapy, if any	Progressed at date of documented PD or death	Progressed at date of documented PD or death
No PD and no death; and new anticancer treatment is not initiated	Censored at last disease assessment	Censored at last disease assessment	Progressed at treatment discontinuation due to reasons other than complete response; otherwise censored at last disease assessment if still on study intervention or completed study intervention

Situation	Primary Analysis	Sensitivity Analysis 1	Sensitivity Analysis 2
No PD and no death; new anticancer treatment is initiated	Censored at last disease assessment before new anticancer treatment	Censored at last disease assessment	Progressed at date of new anticancer treatment

PD=progressive disease; PFS=progression-free survival; the curative surgical resection (details in Section 6.5.3) will be excluded for the new anticancer therapy.

As imaging will continue per protocol Section 6.5.3, participants who have curative surgical resection during the study will be followed for PFS events after surgery until local recurrence, distant metastasis, or death for the primary analysis of PFS. An additional sensitivity analysis will be conducted for PFS in which these participants will be censored at last disease assessment prior to the time of curative surgical resection.

9.6.1.3 Objective Response Rate

The stratified M&N method [Miettinen, O. and Nurminen, M. 1985] will be used for the comparison of the ORR between the 2 treatment groups. The difference in ORR and its 95% CI from the stratified M&N method with strata weighting by sample size will be reported [Miettinen, O. and Nurminen, M. 1985]. The stratification factors used for randomization (Section 6.3.2) will be applied to the analysis.

The point estimate of ORR will be provided by treatment group, together with 95% CI using exact binomial method proposed by Clopper and Pearson [Clopper, C. J. and Pearson, E. S. 1934].

9.6.1.4 **Duration of Response**

If sample size permits, DOR will be summarized descriptively using Kaplan-Meier medians and quartiles. Only the subset of participants who show a CR or PR will be included in this analysis. For each DOR analysis, a corresponding summary of the reasons responding participants are censored will also be provided. Responding subjects who are alive, have not progressed, have not initiated new anticancer treatment, have not been determined to be lost to follow-up, and have had a disease assessment within ~5 months of the data cutoff date are considered ongoing responders at the time of analysis. If a participant meets multiple criteria for censoring, the censoring criterion that occurs earliest will be applied. The censoring rules are summarized in Table 15.

Table 15 Censoring Rules for Duration of Response

Situation	Date of Progression or Censoring	Outcome
No progression nor death, no new anticancer therapy initiated	Last adequate disease assessment	Censor (nonevent)
No progression nor death, new anticancer therapy ^a initiated	Last adequate disease assessment before new anticancer therapy initiated	Censor (nonevent)
Death or progression immediately after ≥2 consecutive missed disease assessments or after new anticancer therapy if any	Earlier date of last adequate disease assessment prior to ≥2 missed adequate disease assessments and new anticancer therapy, if any	Censor (nonevent)
Death or progression after ≤1 missed disease assessments and before new anticancer therapy, if any	PD or death	End of response (Event)

A missed disease assessment includes any assessment that is not obtained or is considered inadequate for evaluation of response.

9.6.1.5 Analysis Strategy for Key Efficacy Endpoints

Table 16 summarizes the primary analysis approach for key efficacy endpoints.

Table 16 Analysis Strategy for Key Efficacy Endpoints

Endpoint	Statistical Method ^a	Analysis Population	Missing Data Approach
Primary Endpoints			
os	Test: Stratified log-rank test Estimation: Stratified Cox model with Efron's tie handling method	ITT (CPS ≥1 and all participants)	Censored at the last known alive date
PFS per RECIST 1.1 by BICR	Test: Stratified log-rank test Estimation: Stratified Cox model with Efron's tie handling method	ITT (CPS ≥1 and all participants)	Primary censoring rule Sensitivity analysis 1 Sensitivity analysis 2 (More details are provided in Table 14, Censoring Rules for Primary and Sensitivity Analyses of PFS)

^a new anticancer therapy: excluding curative surgical resection.

Endpoint	Statistical Method ^a	Analysis Population	Missing Data Approach
Key Secondary Endpoint	t		
Objective response per RECIST 1.1 by BICR	Test and Estimation: Stratified M&N method with sample size weight	ITT (CPS ≥1 and all participants)	Participants without assessments are considered nonresponders and conservatively included in the denominator

BICR=blinded independent central review; CPS=combined positive score; ITT=Intention-to-Treat; M&N=Miettinen and Nurminen; ORR=objective response rate; OS=overall survival; PFS=progression-free survival; RECIST=Response Evaluation Criteria in Solid Tumors.

The strategy to address multiplicity issues with regard to multiple endpoints and interim analyses is described in Section 9.7 (Interim Analyses) and Section 9.8 (Multiplicity).

9.6.2 Statistical Methods for Safety Analyses

9.6.2.1 Overall Safety Assessment

Part 1: Participants will be closely followed for DLTs for 21 days after the first dose of study intervention. Descriptive summary statistics (eg, counts, percentages) will be provided for DLTs by treatment as appropriate. Other safety and tolerability will also be assessed by clinical review of all relevant parameters.

Part 2: The primary safety analyses will include only events that occur prior to Second Course Treatment.

The overall safety evaluation will include a summary by treatment group of the number and percentage of participants with at least one AE, a drug-related AE, an SAE, a serious drug-related AE, a Grade 3 to 5 AE, a drug-related Grade 3 to 5 AE, a discontinuation from study intervention due to an AE, and an AE resulting in death. Point estimates and 95% CIs for the differences between treatment groups in the percentages of participants with the event will be provided based on the criteria described below.

Point estimate and 95% CIs for the difference between treatment groups in the percentage of participants with specific AEs will be provided for AEs that occur in at least 10% of participants in any treatment group. The threshold of at least 10% of participants was chosen because the population enrolled in this study is in critical condition and usually experiences various AEs of similar types regardless of treatment; events reported less frequently than 10% of participants would obscure the assessment of the overall safety profile and add little to the interpretation of potentially meaningful treatment differences. In addition, difference in the percentage of participants with specific Grade 3 to 5 AEs (≥5% of participants in 1 of the treatment groups) will also be summarized by point estimate and 95% CIs.

CIs for between treatment group differences will be provided using the M&N method [Miettinen, O. and Nurminen, M. 1985]. Because many 95% CIs may be provided without

^a Statistical models are described in further detail in the text. For stratified analyses, the stratification factors used for randomization (Section 6.3.2) will be applied to the analysis. Small strata will be combined in a way specified by a blinded statistician prior to database lock for any efficacy interim or final analysis.

adjustment for multiplicity, the CIs should be regarded as a helpful descriptive measure to be used in safety review, not as a formal method for assessing the statistical significance of the between-group differences.

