CBC with Differential ^f	X				X			X	X			X			Х	X	X	X			Will be assessed on Day 1 and Day 22 of C2-C18. Starting from C19 it will be assessed on Day 1 of every cycle.
Chemistry Panel ^f	X			X	X		X	X	X		X	X			x	X	X	X			Will be assessed on Day 1 and Day 22 of C2 and every cycle from C4 onwards.
C-reactive protein ^f	X								X												Screening and Cycle 3 only
Urine Dipstick (Urinalysis) ^{f, g}	х			Х	X		X	X	X		X	X			х	Х	X				At C2 will be assessed at Day 1 and Day 22. After Cycle 3, urine dipstick testing for protein will be performed within 3 days before Day 1 and Day 22 of every cycle while participants are taking lenvatinib.

Study Perioda	Screeningh		Indu	ction	Pha	se (C	Cycle	s)			Conso	lidati	on Ph	ase (C			EOT		sttreati		Notes
Treatment Cycles	Screening			(C1			C2			(C3			C4 to 18	C>18	DC	Safety FU	FU Visits	Survival FU	
Cycle Day	-28 to -1	1	8	15	22	29	36	1 to 36	1	8	15	22	29	36	1 to 36	1 to 36					
Study Week		1	2	3	4	5	6	7 to 12	13	14	15	16	17	18			DC	Days	Every 6 Weeks Post DC	Every	
Scheduled Window (days):		3	±3	±3	±3	±3	±3	±3	±3	±3	±3	±3	±3	±3	±3	±3	±3	±7	±7	±7	
HIV, Hepatitis B and C screen	Х																				Required at baseline. only if mandated by local health authority or as clinically indicated (see Appendix 7).
Thyroid function (T3, T4, and TSH)	X							X	X						X	X	X	X			Should be performed at Day 1 of every Cycle. Free T3 and Free T4 are acceptable. Participants may be dosed while thyroid function tests are pending.
Plasma Sample for Lenvatinib PK		х			х				X												C1D1: 0.5 to 4 and 6 to 10 hours post dose C1D22: predose, and 2 to 12 hours postdose C3D1: predose, 0.5 to 4 and 6 to 10 hours postdose. All predose samples should be collected within 2 hours of lenvatinib administration. Postdose samples are not needed if lenvatinib administration is skipped.

Treatment Cycles Screening C1 C2 C3 C3 C4 to 18 DC Safety FU Visits Visits FU Visits Vis
Study Week 1 2 3 4 5 6 7 to 12 13 14 15 16 17 18
Study Week 1 2 3 4 5 6 7 to 12 13 14 15 16 17 18 DC Days Post Last Post Weeks Dose Every 12 Scheduled Window (days): 3 ±3
Prior to pembrolizumab PK X X X X X Antipembrolizumab Antibodies X X X X X X X X X X X X X
Serum for Pembrolizumab PK X X X Dembrolizumab infusion on C1I and C3D1. Prior to pembrolizumab Antipembrolizumab Antipembrolizumab infusion on C1I Antipembrolizumab Antibodies X X X X X X X X X X X X X
Antipembrolizumab Antibodies X X pembrolizumab infusion on C1I

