 - e. 6-lead ECG is allowed per institutional standard. Induction Phase (CAPOX): ECG at Screening, C1D1, C1D22. C2D1, and C2D22. ECGs in the Induction Phase should be performed approximately 2 hours post lenvatinib dose. Consolidation Phase (CAPOX): C3D1 and C3D22, and starting from C5, an ECG should be performed every 2 cycles (12 weeks). For high-risk participants (as defined in Section 8.3.3), conduct ECG monitoring every cycle. If lenvatinib is discontinued, an ECG is only required at EOT and Safety Follow-up Visits.
 - f. Screening laboratory assessments (PT/INR and aPTT, CBC, chemistry, C-reactive protein and urine dipstick) MUST be performed within 10 days of C1D1 or on C1D1 as long as results are available prior to administration of study intervention. Results from the most recent laboratory tests must be used to assess participant eligibility. After C1, predose laboratory procedures can be conducted up to 72 hours prior to dosing.
 - g. Dipstick is preferred but urinalysis may be used if the use of urine dipstick is not feasible. If a urine dipstick is abnormal follow Section 6.6.3.5. If lenvatinib is discontinued, urine dipstick is only required at EOT visit.
 - h. Pregnancy testing is required at the Safety Follow-up visit and at the end of relevant systemic exposure

1.3.2 Initial Treatment Phase: Lenvatinib Plus Pembrolizumab Plus mFOLFOX6 (Safety Run-in [Part 1] and Main Study [Part 2])

Stu	udy Period ^a	Screening	In	ıduc	ction	ı Ph	ase	(Cy	cles)		C	onsol	idatio	n Pha	ase (C	ycles	s)	EOT	Po	sttreatme	nt	Notes
Trea	atment Cycles	Screening ^b			(C1		•	C2				C3		`	C4 to 18	C>18	DC	Safety FU		Survival FU	
(Cycle Day	-28 to -1	1	8	15	22	29	36	1 to 36	1	8	15	22	29	36	1 to 36	1 to 36					
St	tudy Week		1	2	3	4	5	6	7 to 13	14	15	16	17	18	19			DC	30 Days Post Last Dose	Every 6 Weeks Post DC	12	
	d Window (days):		3	±3	±3	±3	±3	±3	±3	±3	±3	±3	±3	±3	±3	±3	±3	±3	±7	±7	±7	
Administrative P		1																	1	ı		T
Informed Consent	t	X																				Section 8.1.1.1
Reconsent at the fradiographic recur	first indication of rrence/progression																					Assessed by the investigator before the next cycle starts
Inclusion/Exclusion		X																				
Participant Identif	fication Card	X	X																			Update at C1D1
Medical History Prior/Concomitan Treatment Randon	it Medication Review	X	X		X		X		х	X			х			X	х	X	х			At C2 will be assessed on Day 1, Day 15, and Day 29. Will be assessed on Day 1 and Day 22 of C4-C18. See Section 6.5

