Pregnancy Test – Urine or Serum	X	X		X		X		x	x			х			X	X	X	Xh			At C2 will be assessed on Day 1, Day 15, and Day 29. Will also be assessed on Day 1 and Day 22 of C4-C18. WOCBP require a negative pregnancy test within either 24 hours (urine) or 72 hours (serum) before the first dose of study intervention and before each subsequent testing day as indicated. See Section 8.3.6.
FSH (WONCBP only)	X																				After baseline, PT/INR
PT/INR and aPTT ^f	X																				should be tested as needed for participants on warfarin-based anticoagulation therapy.
CBC with Differential ^f	Х			X		X		X	X			X			X	X	X	X			At C2 will be assessed on Day 1, Day 15, and Day 29. Will also be assessed on Day 1 and Day 22 of C4-C18. Starting from C19 it will be assessed on Day 1 of every cycle.
Chemistry Panel ^f	X			X		X		Х	X		X	Х			Х	X	X	X			At C2 will be assessed at Day 1, Day 15, and Day 29. Will be assessed on Day 1 and Day 22 of every cycle from C4 onwards.
C-reactive protein ^f	X								X												Screening and Cycle 3 only

Study Period ^a	Screening	In	duc	tion	ı Ph	ase	(Cyc	eles)		C	onsoli	idatio	n Pha	ase (C		s)	EOT	Po	sttreatme	nt	Notes
Treatment Cycles	Screening ^b			(C1			C2			C	23			C4 to 18	C>18	DC	Safety FU	FU Visits	Survival FU	
Cycle Day	-28 to -1	1	8	15	22	29	36	1 to 36	1	8	15	22	29	36	1 to 36	1 to 36					
Study Week		1						7 to 13	14	15	16	17	18	19				30 Days Post Last Dose	Weeks Post DC		
Scheduled Window (days):		3	±3	±3	±3	±3	±3	±3	±3	±3	±3	±3	±3	±3	±3	±3	±3	±7	±7	±7	
Urine Dipstick (Urinalysis) ^{f. g}	Х			X		Х		X	X		X	X			X	X	X				At C2 will be assessed at Day 1, Day 15, and Day 29. After Cycle 3, urine dipstick testing for protein will be performed within 3 days before Day 1 and Day 22 of every cycle while participants are taking lenvatinib.
HIV, Hepatitis B and C screen	X																				Required at baseline only if mandated by local health authority or as clinically indicated (Appendix 7).
Thyroid function (T3, T4, and TSH)	X							X	X						Х	X	X	X			Should be performed on Day 1 of every Cycle. Free T3 and Free T4 are acceptable. Participants may be dosed while thyroid function tests are pending.

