ECOG Performance Status	X				X			X	X	X			Will be assessed on Day 1 and Day 22 of C2-C18. ECOG Status must be performed within 3 days of beginning of Cycle 1 and prior to each systemic treatment administration.
Poststudy Anticancer Therapy Status									X	X	X	X	
Patient-reported Outcomes													
Tumor Tissue Collection Tumor Blocks or Slides Laboratory Assessments	X												To include PD-L1 and MSI analysis Central PD-L1 result will be masked to the site. A repeat sample will be required if submitted sample is inadequate. The planned MSI sample should be obtained at screening but may be collected post-randomization if needed.
Laboratory Assessments			I					ı .		1	1		W:1111D11D22f-C2-C10
Pregnancy Test – Urine or Serum	X	X			X			X	X	Xg			Will be assessed on Day 1 and Day 22 of C2-C18. WOCBP require a negative pregnancy test within either 24 hours (urine) or 72 hours (serum) before the first dose of study intervention and before each subsequent testing day as indicated. See Section 8.3.6.
FSH (WONCBP only)	X												
PT/INR and aPTT ^e	Х												After baseline, PT/INR should be tested as needed for participants on warfarin-based anticoagulation therapy.
CBC with Differential ^e	X				X			X	X	X			Will be assessed on Day 1 and Day 22 of C2-C18.
Chemistry Panel ^e	X				X			X	X	X			Will be assessed on Day 1 and Day 22 of C2-C18.
C-reactive protein ^e	X							X					Screening and Cycle 3 only
Urine dipstick (Urinalysis) ^{e, f}	X								X				

Study Period	Screening			Treat	tment P	hase			EOT	F	osttreatme	ent	Notes
Treatment Cycles	Screening ^a			(C1			C2 to 18 ^b	DC	Safety FU	FU Visits	Survival FU	
Cycle Day	-28 to -1	1	8	15	22	29	36	1 to 36					
Study Week		1	2	3	4	5	6		DC	30 Days post Last Dose	Every 6 Weeks Post DC	Every 12 weeks	
Scheduled Window (days):		3	±3	±3	±3	±3	±3	±3	±3	±7	±7	±7	
HIV, Hepatitis B and C screen	X												Required at baseline. only if mandated by local health authority or as clinically indicated (see Appendix 7).
Thyroid function (T3, T4, and TSH)	X							X	X	X			Should be performed at Day 1 of every Cycle. Free T3 and Free T4 are acceptable. Participants may be dosed while thyroid function tests are pending.
Efficacy Assessment													

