8.11.3 Treatment Period Visit

Visit requirements are outlined in the SoA (Section 1.3). Specific procedure-related details are provided in Section 8.1, Section 8.2, and Section 8.3.

In the Safety Run-in Phase (Part 1), approximately 12 participants who are eligible for study participation will receive unblinded, open-label treatment with either lenvatinib plus pembrolizumab plus CAPOX or lenvatinib plus pembrolizumab plus mFOLFOX6 chemotherapy.

In the Induction Phase, participants who are eligible for study participation will be assigned to receive unblinded, open-label treatment with lenvatinib plus pembrolizumab plus CAPOX or mFOLFOX6 chemotherapy (Arm 1), or CAPOX or mFOLFOX6 only (Arm 2) chemotherapy.

In the Consolidation Phase, participants will receive lenvatinib plus pembrolizumab only (Arm 1) or CAPOX or mFOLFOX6 (Arm 2).

Lenvatinib will be taken orally once daily, and pembrolizumab will be given by IV infusion on Day 1 of each 42-day cycle, as outlined in Section 8.1.8. CAPOX or mFOLFOX6 chemotherapy will be administered on a 3-weekly or 2-weekly schedule, respectively.

Participants will be scheduled to visit the clinic as follows:

- For lenvatinib plus pembrolizumab plus CAPOX, study visits will occur on Days 1, 15, 22 and 36 of Cycle 1, Days 1 and 22 of Cycle 2; Days 1, 15 and 22 of Cycle 3, and Day 1 and Day 22 of Cycles 4-18. Participants will be contacted by telephone/virtually on Cycle 1, Day 8, Cycle 1 Day 29, and Cycle 3 Day 8.
- For lenvatinib plus pembrolizumab plus mFOLFOX6, study visits will occur on Days 1, 15, and 29 of Cycle 1 and Cycle 2; Days 1, 15 and 22 of Cycle 3, and Day 1 and Day 22 of Cycles 4-18. Participants will be contacted by telephone/virtually on Cycle 1, Day 8 and Cycle 3 Day 8.
- For CAPOX only, study visits will occur on Day 1 and Day 22 of every cycle.
- For mFOLFOX6 only, study visits will occur on Day 1, Day 15 and Day 29 of every cycle.

Due to the differences in visit schedule, once randomized, the participants cannot switch between chemotherapy backbones.

Participants may be seen more frequently, if clinically indicated. Tumor imaging and response assessment will occur every 6 weeks from the day of randomization.

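### Between-arm differences for proteinuria and some other test-detected AEs will partly reflect unequal testing (8 versus 0 scheduled on-treatment dipsticks through Cycle 3), and the safety analysis makes no allowance for it

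*Combined protocol and SAP*

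**What the plan says.** Section 9.6.2.1 plans crude comparisons of incidence: "Point estimate and 95% CIs for the difference between treatment groups in the percentage of participants with specific AEs will be provided". The threshold is 10% in either arm. Specific Grade 3 to 5 AEs are treated the same way at 5%, and Table 17 adds specific serious AEs at 5%. The section calls the intervals descriptive because many are produced without multiplicity adjustment. Table 17 gives lenvatinib clinically significant AEs (CSAEs) no between-group interval. Section 9.6.2 does not mention unequal testing.

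The Schedules of Activities (Section 1.3) set different testing by arm. For Arm 1 on CAPOX the dipstick note reads "At C2 will be assessed at Day 1 and Day 22. After Cycle 3, urine dipstick testing for protein will be performed"; for Arm 1 on mFOLFOX6 it begins "At C2 will be assessed at Day 1, Day 15, and Day 29. After Cycle 3, urine dipstick testing for protein". After Cycle 3 the Arm 1 rule is "urine dipstick testing for protein will be performed within 3 days before Day 1 and Day 22 of every cycle while participants are taking lenvatinib", and footnote g of Section 1.3.1 adds: "If lenvatinib is discontinued, urine dipstick is only required at EOT visit". In Sections 1.3.3 and 1.3.4 the Arm 2 dipstick row is marked only at Screening and end of treatment (EOT).

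Visits differ too. Section 8.11.3 states "For CAPOX only, study visits will occur on Day 1 and Day 22 of every cycle", whereas in Arm 1 with CAPOX "study visits will occur on Days 1, 15, 22 and 36 of Cycle 1". Appendix 3 lets an abnormal urinalysis, ECG or vital sign count as an AE if the investigator judges it clinically significant.

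**The concern.** A percentage of participants with a test-detected event depends on how often the test is done. If one arm is tested repeatedly on treatment and the other only at EOT, transient findings are recorded mainly in the first. The difference and its interval then partly measure the schedule. Safety versus chemotherapy is a stated secondary objective, so this affects how the added toxicity of the combination is described.

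Proteinuria is likely to reach the tables. Section 2.1 reports Grade 3 or higher proteinuria of 17% and hypertension of 38% in the Phase 2 study of lenvatinib plus pembrolizumab. The thresholds apply if either arm crosses them, so extra testing in Arm 1 also influences which events receive an interval.

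**Working it through.** **Step 1: count scheduled tests.** The plan states no totals, so there is no figure to reproduce. Inputs are the marked days in Sections 1.3.1 to 1.3.4, with Cycle 2 days taken from the row notes and footnotes. In Arm 2, Cycles 2 to 18 repeat the Cycle 1 visits. Screening and EOT are excluded; the count stops at the end of Cycle 3.

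- Dipsticks, Arm 1 CAPOX: C1 Days 15, 22, 36 (3) + C2 Days 1, 22 (2) + C3 Days 1, 15, 22 (3) = 8.
- Dipsticks, Arm 1 mFOLFOX6: C1 Days 15, 29 (2) + C2 Days 1, 15, 29 (3) + C3 Days 1, 15, 22 (3) = 8.
- ECGs, Arm 1: two in each of Cycles 1 to 3 on either backbone = 6.
- Dipsticks and ECGs, Arm 2: none between Screening and EOT.

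| Scheduled on treatment, C1 to C3 | CAPOX, Arm 1 vs Arm 2 | mFOLFOX6, Arm 1 vs Arm 2 |
|---|---|---|
| Urine dipstick | 8 vs 0 | 8 vs 0 |
| ECG | 6 vs 0 | 6 vs 0 |
| BP/vital-sign contacts | 12 vs 6 | 11 vs 9 |
| Chemistry | 8 vs 5 | 8 vs 8 |
| CBC | 5 vs 5 | 7 vs 8 |
| Thyroid | 2 vs 2 | 2 vs 2 |

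At EOT both arms have a dipstick and an ECG, and both have an ECG at Safety Follow-up. Only Arm 1 has an EOT LVEF.

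**Step 2: scale, for dipsticks only.** The documents give no per-test positivity, so the following is an assumption. Let each dipstick be positive with probability q, equal in both arms (no drug effect). Counting the EOT test, Arm 1 has 8 + 1 = 9 tests and Arm 2 has 1.

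- Independent tests: the proportion ever positive is 1 − (1 − q)^k.
  - q = 2%: 1 − 0.98^9 = 16.6% versus 2.0%, a difference of 14.6 points.
  - q = 5%: 1 − 0.95^9 = 37.0% versus 5.0%, a difference of 32.0 points.
- Fully persistent positivity: nine tests find the same people as one, so the difference is 0.

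With 880/2 = 440 per arm and counts rounded to whole participants, the Miettinen-Nurminen 95% intervals in the independent case are 11.0 to 18.5 points (q = 2%) and 27.1 to 37.0 points (q = 5%). Under that assumption the interval excludes zero through test count alone.

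**The case against.** A reader might infer that Arm 1 is monitored more closely across the board and that toxicity in Arm 2 simply went unlooked for. The documents do not support this. CBC and thyroid testing are essentially equal, and chemistry on mFOLFOX6 is 8 versus 8. Arm 2 has vital signs at every treatment visit, a dipstick at EOT, and ECGs at EOT and Safety Follow-up. Appendix 7 requires ECGs around each oxaliplatin infusion at French sites, in either arm. From Cycle 4 the mFOLFOX6 visit pattern reverses: Days 1 and 22 in Arm 1, Days 1, 15 and 29 in Arm 2. AE reporting is continuous in all four schedules, so contact days do not limit it. These points stand and they narrow the concern.

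It also stands that a genuine excess is expected, since Section 6.6.4.1 names hypertension and proteinuria as lenvatinib risks. The full Arm 1 dipstick count applies only while lenvatinib continues, unscheduled tests are possible in both arms, and nothing shows that QT or LVEF events would reach a threshold.

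Three replies do not remove the problem. Calling the intervals descriptive addresses multiplicity, and a descriptive estimate can still be biased. Withholding an interval for CSAEs does not stop proteinuria getting one as a specific AE. Looking only at Grade 3 or above does not help for proteinuria either: in Section 6.6.3.5 the triggers for quantitative urine collection are tied to receiving lenvatinib, and Arm 2 has no scheduled on-treatment dipstick to start that pathway.

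**Conclusion.** The concern holds for specific tests. It applies most clearly to dipstick-detected proteinuria on both backbones. It applies to ECG-detected events and LVEF decrease if they reach a reporting threshold, and to a lesser extent to BP- and chemistry-detected events on CAPOX. It does not extend to cytopenias or thyroid abnormalities.

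The size cannot be fixed from the documents. The range of about 0 to about 15 points (q = 2%) or 32 points (q = 5%) concerns dipstick positivity through Cycle 3 plus EOT. It rests on assumed positivity, equal rates in both arms and lenvatinib continuing. For AEs it would be smaller, because only clinically significant findings count. The upper figures should not be read as an expected bias, nor the whole Arm 1 excess as an artefact. Efficacy conclusions are unaffected. The supplemental SAP was not available and might address the point.

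**What to change.** Leave all procedures unchanged. In Section 9.6.2.1 and Table 17:

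1. Report proteinuria, QT-prolongation and LVEF-decrease AEs as counts and percentages by arm without a between-arm interval, as Table 17 already does for lenvatinib CSAEs. Add a footnote giving the scheduled dipsticks, ECGs and LVEF assessments in each arm, including the French ECG requirement.
2. Add a supportive between-arm comparison, within backbone, of worst post-baseline laboratory grade (ALT/AST and other chemistry) and of blood pressure. Use recorded values only from visits in the first 12 weeks at which the test is scheduled in both arms: Days 1 and 22 for CAPOX; Days 1, 15 and 29 for mFOLFOX6. After baseline this means C1 Day 22 and C2 Days 1 and 22 for CAPOX, and C1 Days 15 and 29 and C2 Days 1, 15 and 29 for mFOLFOX6. Recorded values are needed because continuously reported AEs cannot be assigned to a visit day.

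The introduction to Section 9 allows such a change through the supplemental SAP before any planned analysis is conducted; after that it should be identified as post hoc in the CSR. The cost is SAP wording and a few tables from data already collected. The downside is fewer events and less precision in the supportive comparison.
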